#### 6.7.2 UNANTICIPATED PROBLEMS REPORTING

Unanticipated problems that are serious adverse events (SAEs) will be reported by the investigator to the SDSU IRB within 24 hours. Unanticipated problems which can cause serious risks to others are reported to the NIMH PO and the DSMB within 10 business days of the investigator learning of the event. Any other unanticipated problem will be reported by the investigator to the SDSU IRB, the NIMH PO, and the NIMH DSMB within 10 business days.

The unanticipated problem report will include the following information:

- Protocol identifying information: protocol title and number, PI's name, and the IRB project number
- A detailed description of the event, incident, experience, or outcome
- An explanation of the basis for determining that the event, incident, experience, or outcome represents an unanticipated problem
- A description of any changes to the protocol or other corrective actions that have been taken or are proposed in response to the unanticipated problem

---

#### 6.7.3 REPORTING UNANTICIPATED PROBLEMS TO PARTICIPANTS

Participants will be informed individually about unanticipated problems which may impact their current and future health and privacy via their preferred method of communication (e.g. phone, text, mail).

## 7 STATISTICAL CONSIDERATIONS

### 7.1 STATISTICAL HYPOTHESES

- Primary Endpoint(s):

The purpose of the case series is to obtain feedback on study procedures and the PN+SPI intervention. Therefore, there are no formal hypotheses associated with the case series. Only descriptive statistics will be calculated.

For the open trial, it is hypothesized that PN+SPI participants will display decreases in thwarted belongingness and increases in suicide-related coping skills (the hypothesized mechanistic targets of the intervention). We will also assess the feasibility and acceptability of the PN+SPI intervention during the open trial.

### 7.2 SAMPLE SIZE DETERMINATION

For the open pilot, N = 30 was selected based on recommendations in the field which specify 15 to 30 participants per condition are satisfactory for pilot trials. Given the open pilot includes a single condition, we planned for the upper limit sample size based on these recommendations.

### 7.3 POPULATIONS FOR ANALYSES

There are no quantitative analyses for the case series. For the open pilot, the analysis population will include any participant who participated in one or more intervention sessions. Given that the first intervention session occurs during the initial baseline appointment, this means that all participants should be included in the analyses.

### 7.4 STATISTICAL ANALYSES

#### 7.4.1 GENERAL APPROACH

In the case series and open trial, descriptive statistics will be presented as frequencies and percentages (for binary and categorical variables), means with standard deviations, and range (for continuous variables).

In the open trial, qualitative data will be saved in a text file to import into NVivo for analysis. Drs. [name] and [name] will review the qualitative data using a content analysis technique, which identifies emergent themes occurring during discussion. Code mapping will be used to develop a preliminary set of codes (themes) corresponding to each potential strength of the PN+SPI as well as every potential aspect for improvement. Then, Drs. [name] and [name] will independently code the remaining data and meet to discuss coding. Once coded, the data will be summarized by theme.

Inferential tests and checks of assumptions underlying statistical procedures will not be performed in either the case series or open trial. No corrective procedures will be applied.

#### 7.4.2 ANALYSIS OF THE PRIMARY ENDPOINT(S)

As the purpose of the case series is to obtain feedback on study procedures and the PN+SPI intervention, no statistical analyses will be conducted.

In the open trial, the feasibility and acceptability of the PN+SPI intervention will be assessed descriptively and therefore will not involve any statistical analyses. However, we will examine the preliminary impact of the PN+SPI intervention on the purported mechanisms of action (e.g. decreasing thwarted belongingness, increasing suicide-related coping skills). This will be done by testing within-person changes in thwarted belongingness and suicide-related coping skills by calculating Cohen's d. If missing data are minimal (e.g. 5% or less) available item analysis will be conducted. If greater than 5% of data are missing, multiple imputation will be conducted. Outliers will be defined as  $\pm 3.3$  standard deviations from the mean and will be Winsorized to the next highest non-outlier value. This approach retains the rank order of the outlier, without the outlier exerting a disproportionate effect on the sample.

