lesbian, bisexual, pansexual, asexual, queer); and/or 2) report same-gender attraction; and/or 3) identify as a gender different than their birth sex (e.g. transgender, gender non-binary, genderqueer). Despite the fact that SGMs are at a high risk of suicide attempts and death by suicide, no known suicide prevention programs exist for this vulnerable population. Therefore, the purpose of the present study is to develop and test a novel suicide prevention intervention designed to reduce suicide attempts among SGM youth and emerging adults. The proposed intervention will integrate a single-session, empirically supported suicide prevention intervention (Safety Planning Intervention; SPI) with patient navigation (PN) services (PN+SPI). PN may be particularly well suited to address the needs to young SGMs at risk of suicide, given its focus on cultural sensitivity and its high level of flexibility to address patients' specific needs. Patient navigators work with the individual patient, the patient's significant others, the health care system, and community services to improve adherence to recommended health care and healthy behaviors. The SPI is a 30-minute behavioral intervention to reduce suicide attempts by providing individuals with specific actionable behaviors they can engage in to reduce the likelihood of acting on suicidal urges, including: 1) identification of suicidality warning signs; 2) implementing personal coping strategies; 3) connecting with mental health professionals; 4) connecting with friends and/or family for support; 5) connecting with mental health professionals; and 6) reducing access to means of completing suicide. Patient navigators will deliver the SPI and continue frequent contact for the purpose of providing motivational enhancement, problem-solving, reinforcing coping strategies, and connecting participants to social support and mental health resources (e.g. SGM-specific support groups from the community). The aims of this R61 phase are to refine the PN+SPI intervention content and procedures, assess acceptability and feasibility, and test if the intervention impacts propertied targets (i.e. thwarted belongingness and suicide-related coping skills). The first phase of the R61 study is to conduct a case series and the second phase is to conduct an open-phase trial. The case series will be used to obtain participant feedback on study procedures and the PN+SPI intervention for the purpose of improving approaches for the open-phase trial. Thus, it has no hypotheses. Based on the minority stress model and the interpersonal theory of suicide, in the open-phase trial, we hypothesize that the PN+SPI intervention will reduce suicide attempts through 2 proposed targets: 1) decreasing thwarted belongingness (e.g. through interactions with the PN and connection with SGM-specific support groups) and 2) increasing suicide-related coping skills. The PN+SPI overtly develops with participants both internal and external coping skills to rely on during suicidal crises. For example, internal coping skills refers to distraction from suicidal thoughts and urges, whereas external coping skills refers to means restricting (i.e. restricting access to lethal means to act on suicidal urges) in addition to reaching out to others (e.g. friends, family, PN, mental health provider) when in crisis. Therefore, the clinical outcome of interest are effect size estimates of changes in thwarted belongingness and suicide-related coping.

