### 3.3 END-OF-STUDY DEFINITION

In the case series, a participant is considered to have completed the study if they have completed the baseline assessment, at least 1 intervention session, and the 3-month follow-up assessment. In the open trial, a participant is considered to have completed the study if they have completed the baseline assessment, at least 1 intervention session, and the 3-month and 6-month follow-up assessments.

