An electronic tracking system will be developed for use by the project director and outcome assessors that will track participants in order to schedule and complete follow-up assessments. This system will provide the outcome assessors with a calendar of participants to contact for follow-up visits within one month of each's participant's next scheduled follow-up appointment (if they are unable to schedule the follow-up appointment at the time of the previous appointment). The outcome assessors will be responsible for documenting both baseline and each follow-up data collection encounter in the system. At the baseline assessment participants will complete a locator form which asks permission for study staff to contact participants via phone, text, email,

social media (Facebook) and mail. We also ask participants for their preferred contact method, although we will use multiple methods of contacting participants, as necessary. Additionally, we ask participants for the name and contact information of close friends/family member whom the study could contact in the event that staff are unable to connect with the participant. We also provide evening and weekend appointments to accommodate participants' schedules. Further, we provide phone/text reminders regarding study appointments and confirm appointments with participants several times in advance. Participants will be provided with incentives (compensation via gift cards) to participate in each data collection session. These incentives will be provided in recognition of the time and effort the participant is providing to the study team, as well as costs for travel. The study team will meet weekly to discuss study enrollment and retention rates, as well as challenges faced in both recruitment and retention. These challenges, as well as the steps taken to overcome them, will be part of the feasibility data collected by the study team. However, it is expected that these strategies will prove successful based on our previous history using them. For example, in [name] and [name]' ongoing R34 HIV prevention trial sampling young sexual minority men in the San Diego area, the project team has retained 100% of our sample 6 months post-baseline.

This grant is focused on recruiting and retaining participants from historically under-represented populations. We will be using strategies for recruitment and retention which have been optimized in other studies (described above).

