## 6 STUDY INTERVENTION/EXPERIMENTAL MANIPULATION DISCONTINUATION AND PARTICIPANT DISCONTINUATION/WITHDRAWAL

### 6.1 DISCONTINUATION OF STUDY INTERVENTION/EXPERIMENTAL MANIPULATION

If a subject chooses to discontinue from PN+SPI intervention but agrees to remain in the study, remaining study procedures (assessments) will be completed as indicated by the study protocol.

The data to be collected at the time of study intervention discontinuation will include the following:

- The reason(s) for discontinuing the participant from the intervention, and methods for determining the need to discontinue
- If the participant is due to complete assessments within 2 weeks of being discontinued from the study intervention, those assessments will be administered at the time of discontinuation; if the next scheduled assessments are more than 2 weeks from the discontinuation date, the discontinued participant will wait for the next scheduled assessment. Thereafter, the participant will be included in all future scheduled assessments, even though not participating in the intervention.

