### 6.3 LOST TO FOLLOW-UP

For the case series, a participant will be considered lost to follow-up only if they fail to complete the three-month follow-up assessment within 31 days of when it was scheduled to be completed. For the open trial, a participant will be considered lost to follow-up only if they fail to complete the six-month follow-up assessment within 31 days of when it was scheduled to be completed. Otherwise, study staff will continue to attempt to contact the participant, unless the participant decides to withdraw from the study or 31 days has passed following the last scheduled follow-up.

The following actions will be taken to minimize loss to follow-up and missing data:

- At the baseline assessment, participants will complete a locator form, which asks permission for study staff to contact participants via phone, text, email, and mail. We also ask participants for their preferred contact method, and for the name and contact information of close friends/family member whom the study could contact in the event that staff are unable to connect with the participant. Study staff will utilize these multiple contact methods to schedule, or re-schedule, follow-up assessments as necessary.
- Study staff will contact participants on multiple days and times.
- Participants will be given multiple appointment reminders and study staff will confirm the scheduled appointment with the participant multiple times.
- Study staff will contact participants to schedule follow-up appointments within a month of each participant's next scheduled follow-up appointment (if they are unable to schedule the follow-up appointment at the time of the previous appointment).
- Upon rescheduling follow-up assessments, study staff will counsel the participant on the importance of maintaining the assigned visit schedule and ascertain if the participant wishes to continue in the study.
- The study team will meet weekly to discuss challenges faced in contacting participants and completing follow-up assessments and how to potentially overcome them.

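### Does the 5% missing-data rule in Section 7.4.2 need a stated unit before the open-trial effect sizes can be relied on?

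*Combined protocol and SAP*

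**What the plan says.** The open trial has 30 participants (Section 7.2), assessed at baseline, month 3 and month 6. Section 7.4.2 looks at the preliminary effect on the two targets by "testing within-person changes in thwarted belongingness and suicide-related coping skills" through Cohen's d. For missing values it has two branches: "If missing data are minimal (e.g. 5% or less) available item analysis will be conducted" and "If greater than 5% of data are missing, multiple imputation will be conducted". No section gives a denominator, or says whether the percentage is pooled, per visit or per outcome. The lower-branch figure is offered only as an example.

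Two other sections classify participants by the visits they attend. Section 3.3 counts an open-trial participant as having completed the study after the baseline assessment, "at least 1 intervention session, and the 3-month and 6-month follow-up assessments". Section 6.3 says that "a participant will be considered lost to follow-up only if they fail to complete the six-month follow-up assessment" within 31 days of its due date. Section 7.4.2 refers to neither.

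Section 2.1 states that "the clinical outcome of interest are effect size estimates of changes in thwarted belongingness and suicide-related coping". Section 7.4.1 rules out inferential tests.

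**The concern.** A rule that switches method at a threshold should give every analyst the same answer on the same data. This one need not. At N = 30 each participant is 3.3%, so a second missed visit crosses 5% on a participant count but stays well below it on a visit count. Sections 3.3 and 6.3 seem to make this worse: if one participant misses only month 3 and another only month 6, there are two non-completers (2/30 = 6.7%) but one person lost to follow-up (1/30 = 3.3%).

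Scoring from available items also does nothing for a visit missed entirely, because there are no items to score. The change score is then absent and that d rests on fewer than 30 people. Above 5%, the imputation predictors are not named.

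Since d is the main quantitative result, the worry is that the method could be chosen after the data are seen, and that the choice could move d.

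**Working it through.** **1. Does the unit change the branch?** Inputs: 30 participants, 30 × 2 = 60 follow-up visits, 30 × 3 = 90 person-visits. For m people who miss month 6 only:

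| m | m/30 | m/60 | m/90 |
|---|---|---|---|
| 1 | 3.3% | 1.7% | 1.1% |
| 2 | 6.7% | 3.3% | 2.2% |
| 3 | 10.0% | 5.0% | 3.3% |
| 4 | 13.3% | 6.7% | 4.4% |
| 5 | 16.7% | 8.3% | 5.6% |

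The units disagree at m = 2, 3 and 4 and agree otherwise. An item count is a further reading: 15 × 30 × 3 = 1,350 INQ-15 items.

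**2. How often would they disagree?** The plan gives no expected loss, so the rates here are assumptions. If people miss month 6 only, independently at rate p, disagreement has probability P(2 ≤ m ≤ 4) with m ~ Binomial(30, p). If people who leave miss both follow-ups, the fractions are m/30, 2m/60 and 2m/90; only m = 2 divides them (6.7%, 6.7%, 4.4%), so the probability is P(m = 2).

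| p | month 6 only | both visits |
|---|---|---|
| 1% | 0.04 | 0.03 |
| 2% | 0.12 | 0.10 |
| 5% | 0.43 | 0.26 |
| 10% | 0.64 | 0.23 |
| 15% | 0.48 | 0.10 |

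Mixed patterns with 5% to 10% month-6 loss, including some month-3 losses, gave 0.29 to 0.51 (400,000 simulated trials each). So disagreement is uncommon at very low loss and quite possible at moderate loss.

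**3. Does the branch move d?** Assumed: n = 30, all correlations 0.6, true d = 0.5 at both follow-ups, m = 2, 3 or 4 missing at month 6, 3,000 trials, 20 imputations from baseline and month 3. Selection, where present, uses weight exp(∓x). Differences are observed-only d minus imputed d:

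- Random loss: 0.518 − 0.516, 0.523 − 0.519, 0.517 − 0.512 = 0.002, 0.004, 0.005. Within a single trial the mean absolute difference is 0.025, 0.031, 0.035.
- Low month-3 score lost: 0.524 − 0.521, 0.517 − 0.512, 0.513 − 0.506 = 0.003, 0.005, 0.007.
- Poor month-3 change lost: 0.548 − 0.512, 0.563 − 0.507, 0.589 − 0.516 = 0.036, 0.056, 0.073.
- Good month-3 change lost: 0.485 − 0.510, 0.474 − 0.511, 0.451 − 0.500 = −0.025, −0.037, −0.049.

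**4. Compared with the precision of d.** SE = √(1/n + d²/2n) = √(1/30 + 0.25/60) = 0.194. If d is standardised by the baseline SD with correlation 0.6, SE = √(0.8/30 + 0.25/60) = 0.176. The largest gap, 0.073, is about 0.4 of either.

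**5. The lower branch with one missed visit.** Suppose 29 observed changes have mean 0.5 and SD 1, and the absent change is x. The full mean is (14.5 + x)/30 and the full SD is √{[28 + (29/30)(x − 0.5)²]/29}. For x = −0.5, 0 and 1 this gives d = 0.467/0.999 = 0.47, 0.483/0.987 = 0.49 and 0.517/0.987 = 0.52, against 0.50 from the 29.

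**6. Sections 3.3 and 6.3.** One says who has finished the study; the other says when staff stop pursuing someone. A participant who misses month 3 and attends month 6 is a non-completer and is not lost; both statements hold. The missing-data rule uses neither status, so their difference does not drive the switch.

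**The case for a change.** The best case for a change is that d is the clinical outcome of interest, that one sentence would close the gap, and that methods should be fixed before data are seen. The facts behind it stand: no unit is stated, and at moderate loss different readings often pick different methods. It is also right that speaking of items and of data only hints at an item-level or data-point reading; it does not define one, and it leaves a wholly missed visit unaddressed.

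What does not follow is that the result is at risk. The differences of 0.02 to 0.07 need strong selection on month-3 change, which nothing in the documents suggests. The design also works against large loss: the investigators report that in a related local trial "the project team has retained 100% of our sample 6 months post-baseline", and Section 6.1 keeps those who stop only the intervention under assessment ("the participant will be included in all future scheduled assessments, even though not participating in the intervention"). That retention comes from another population and cannot be assumed here, but the conclusion does not rest on it.

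The more ambitious remedy, imputing every missed visit whatever the percentage, would replace the planned rule instead of clarifying it. With 30 people, whether that improves on the observed cases is debatable. Naming the imputation predictors and adding a zero-change sensitivity analysis are good practice, but they repair no error.

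**Conclusion.** The unit of the 5% rule is missing and no other section supplies it, so two to four missed month-6 visits can lead to either method. That is a gap in detail, and no change to the plan is needed. Both branches are defensible for a descriptive effect size. They agree on average to within 0.01 under random loss or loss tied to a low month-3 score, and differ by at most about 0.07 under the strongest selection tried, against a standard error of about 0.19. The open trial makes no inferential test, its sample size does not depend on d, and neither the protocol nor the SAP section ties the move to a later randomised phase to a value of d. The apparent clash between Sections 3.3 and 6.3 is not one.

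These sizes rest on assumed loss rates, correlations of 0.6 and a true d of 0.5. How often the readings disagree depends heavily on the assumed pattern of loss; the small effect on d depends on it much less. An analyst who picks a reading before looking at the outcomes and reports the number observed behind each d will have dealt with the matter.

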#### 7.4.3 BASELINE DESCRIPTIVE STATISTICS

In both the case series and open trial, baseline descriptive statistics will be used to describe the sample in terms of sociodemographics and psychiatric diagnoses. There is only one treatment group (PN+SPI) so intervention groups cannot be compared. Inferential statistics will not be used.

### 8 SUPPORTING DOCUMENTATION AND OPERATIONAL CONSIDERATIONS

#### 8.1 REGULATORY, ETHICAL, AND STUDY OVERSIGHT CONSIDERATIONS

##### 8.1.1 INFORMED CONSENT PROCESS

###### 8.1.1.1 CONSENT AND OTHER INFORMATIONAL DOCUMENTS PROVIDED TO PARTICIPANTS

For both the case series and open trial, participants will initially be screened for eligibility via a phone screen conducted by a trained member of the study team. Prior to beginning the phone screen, a trained member of the study team will obtain verbal consent for pre-enrollment screening. The IRB-approved verbal informed consent form will be read verbatim to all study participants over the phone. It describes in detail the phone screening procedure and associated risks. During the COVID-19 pandemic, all study procedures, including consenting, will be conducted virtually.

Those who meet the screening criteria will be scheduled for an initial baseline appointment. At the time of the baseline appointment, a trained member will engage in a discussion with all participants and using a written/digital informed consent form that describes in detail the study intervention, study procedures, information about potential risks and benefits of participation, and information regarding whom they can contact if they have any further questions. It will also state that participation is voluntary, that participants can refuse to answer any question, they can withdraw from the study at any time, and that study participation is in no way related to participating in other studies at San Diego State University. Written/digital documentation of informed consent will be completed prior to starting the intervention. The following consent materials are submitted with this protocol:

1. Telephone Screening Consent (**see attachment 6**)
2. Informed Consent Case Series (**see attachment 7**)
3. Informed Consent Open Trial (**see attachment 8**)

